Modification: We are requesting to modify section 10.2.1 of the protocol to indicate that we have decided that no usual care clinics (i.e. comparator clinics) will be included from the two health systems that are not in the trial but are only providing data on exemplar sites. Instead, we will compare the exemplar sites to the intervention sites adjusting for the baseline values of the outcomes at the same site.

Rationale: The rationale for this modification is that after extensive exploration, there are not appropriately similar comparator clinics in the two health systems, and the exemplar clinics drew from multiple clinics so that there would be cross-over/contamination between the exemplar clinics and any

similar clinics. This is in part because Colorado and Oregon have large rural areas and the exemplar clinics served their urban areas. Given differences in the available comparator clinics, they were deemed not comparable. For example, if we selected a comparator clinic that was close to the exemplar clinic, the measured OUD treatment in the comparator clinic could be artificially low if patients who were originally members of the selected comparator clinic transferred their care to the exemplar clinic. On the other hand, if we selected a comparator clinic that was far from the exemplar clinic, there would likely be a large number of differences in the two clinics due to geographical heterogeneity in patient characteristics and treatment provision (e.g. urban exemplar vs rural).

Modification #23 (Date: 11/16/2020)

Original protocol: This modification augments (and therefore supersedes) modification #15 above regarding extending the intervention period from 2-years to 3-years.

Modification: This modification is to request to extend the original 2-year intervention period to a 3-year intervention period. We would like to extend the time the nurse care managers (NCMs) are working in the clinics implementing the PROUD intervention by 12 months with continued support by the Technical Assistance Team. There will be no changes to the main trial analyses as we will still analyze outcomes of the trial as proposed in the protocol with a 2-year intervention period. In addition, a final data extraction will be added, after the 3-year intervention period ends on 2/28/2021, to allow us to conduct secondary analyses of the primary outcome, as well as other secondary analyses.

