We are requesting to add study objectives to secondarily evaluate the impact of extending the intervention period. We have also added secondary objectives to reflect the changed circumstances after COVID hit the U.S. in March 2020.

Added Secondary Objectives:

To evaluate the primary outcome* of the PROUD trial over 3 years follow-up (*days of OUD treatment). This objective will involve replicating the main trial analyses 1 year after the end of the main PROUD trial (after 3 years post-randomization for 5 sites and 2.5 years post-randomization for 1 site).

Secondarily, if the PROUD intervention has an impact on the main outcome (days of OUD treatment over 2 years follow-up), we will evaluate whether time—before or after 3/1/2020—modified the effect of the PROUD intervention on the main outcome:

- a. In the year before and after 3/1/2020 and;
- b. In the 6 months before and after 3/1/2020 (before 2 NCMs left the intervention clinics).

Rationale: Recent data has revealed that the MA model of collaborative care that we are testing often takes more than 2 years to achieve steady recruitment rates of 1-2 patients a week. Therefore, NIDA decided that it was appropriate to test the PROUD intervention for 3 years in addition to main analyses of the trial after 2 years. Extending the intervention to 3-years will assist in seeing the full effect of the PROUD Trial intervention. Limiting the trial to 2 years might have led the NCMs to leave as the study ended, further undermining our ability to assess the effectiveness of the MA model. In addition, COVID hit the U.S. in March 2020 as the third year began. We therefore would like to take advantage of this

extension to evaluate the impact of COVID secondarily (testing whether any impact of the intervention was modified after 3/1/2020).

Modification #24 (Date: 11/16/2020)

Original protocol: The original protocol stated that the study did not include any interviews or surveys of primary care staff. The protocol was modified in March 2018 to include an anonymous 1-page survey at baseline of clinic staff's opinions on treating opioid addiction in primary care (modification #4 in the protocol).

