3.1.7 The MA Model Improves Not Only Access but Quality

The MA Model of collaborative care for OUDs appears to increase both access and retention in treatment,^{1,47,65} a strong predictor of outcomes.⁶⁹ In contrast the Hub and Spoke Model has not been shown to improve retention in treatment. Based on reports from Massachusetts and Harborview Medical Center in Seattle that implemented the MA Model in 2016, only 7-30% of patients with OUDs treated with buprenorphine were PC patients in clinics before they sought OUD treatment. Moreover, the MA Model results in high rates of long-term engagement: 51% and 67% of patients remain engaged in OUD treatment at 12 months in care: in 2 case series of 408 and 7,722 patients with OUDs, respectively.^{1,47} Retention is a major predictor of health outcomes, as demonstrated in the Pennsylvania Medicaid program where only 21% of patients had persistent treatment at 1 year, but those with persistent treatment had lower rates of hospitalizations and ED visits than patients who left treatment sooner.⁷⁰

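### The before/after-3/1/2020 contrast in Modification #23 is confounded with ramp-up of the intervention and cannot support a statement about the impact of COVID

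*Protocol*

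**What the plan says.** Modification #23 adds two objectives. One repeats the main analysis over three years. The other applies "if the PROUD intervention has an impact on the main outcome (days of OUD treatment over 2 years follow-up") and asks whether calendar time modified the effect on days of OUD treatment. It has two windows:

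- (a) "In the year before and after 3/1/2020 and";
- (b) "In the 6 months before and after 3/1/2020 (before 2 NCMs left the intervention clinics").

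The rationale presents this as an "extension to evaluate the impact of COVID secondarily (testing whether any impact of the intervention was modified after 3/1/2020"). It also says that "COVID hit the U.S. in March 2020 as the third year began" and that the model "often takes more than 2 years to achieve steady recruitment rates of 1-2 patients a week".

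No model, effect scale, significance level or term for time since randomization is given. The SAP does not fill the gap: its follow-up (SAP 2.4) stops at two years and it contains no COVID analysis. Modification #23 is therefore the operative text for this objective, not a record of replaced wording.

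**The concern.** The question posed is whether the pandemic changed the intervention effect. The contrast planned measures any change in the effect across 3/1/2020, whatever its cause. Time since randomization advances with the calendar, and the protocol expects the intervention to be still growing at that point.

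The concurrent UPC arm protects against influences that both arms share. It does not protect against ramp-up, which occurs only in the intervention arm.

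The outcome adds to the problem. Under SAP 4.1.1 it sums all covered days, so it measures the stock of patients on treatment rather than the flow of new starts. A stock that has not reached equilibrium keeps rising under constant starts, and it falls slowly if starts cease. Real harm to recruitment could thus be reported as no modification, and ordinary growth could be reported as a changed effect in the COVID period.

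**Working it through.** **Plan's own figure.** None is stated for this contrast. The nearest is the 84% power at a 1.30-fold increase in SAP Table 5, which re-simulates at 83.9%. It concerns a different comparison and does not bear on this one.

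**Position of the split.** The added data extraction comes "after the 3-year intervention period ends on 2/28/2021", so 3/1/2020 is month 24 at the five on-time HCSs. The sixth was randomized 6 months late, so there it is month 18.

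| Window | Five HCSs | Late HCS |
|---|---|---|
| (a) | months 12-24 v 24-36 | months 6-18 v 18-30 |
| (b) | months 18-24 v 24-30 | months 12-18 v 18-24 |

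**Inputs.** Start-up is 6 months (Protocol 7.1.1). For retention, Protocol 3.1.7 reports that "51% and 67% of patients remain engaged in OUD treatment at 12 months in care".

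**Assumptions.** Starts are constant from month 6, exit is exponential, UPC has no corresponding ramp, and COVID has no effect.

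**Model.** With r starts per week, 12-month retention R and h = -ln(R), the number on treatment at t years is

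N(t) = (52r/h) x (1 - exp(-h(t - 0.5))).

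The mean over a window from a to b, per unit of 52r, is

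M(a,b) = (1/h) x [1 - (exp(-h(a - 0.5)) - exp(-h(b - 0.5))) / (h(b - a))].

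The start rate cancels from the after/before ratio.

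**No COVID effect, five on-time HCSs.**

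| R | h | M(1,2) | M(2,3) | Ratio (a) | M(1.5,2) | M(2,2.5) | Ratio (b) |
|---|---|---|---|---|---|---|---|
| 51% | 0.673 | 0.713 | 1.092 | 1.53 | 0.842 | 1.026 | 1.22 |
| 67% | 0.400 | 0.813 | 1.369 | 1.68 | 0.981 | 1.256 | 1.28 |

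At the late HCS, window (a) gives 0.934/0.404 = 2.31 at 51% and 1.118/0.439 = 2.55 at 67%.

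**Starts stop on 3/1/2020.** At 51% retention, patients already on treatment contribute 0.687 in year 3, and a full year of new starts would add 0.404.

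- A total stop gives 0.687/0.713 = 0.96 in (a).
- A 90% cut gives (0.687 + 0.040)/0.713 = 1.02.
- The cut that makes year 3 equal to year 2 is 1 - (0.7133 - 0.6871)/0.4044 = 0.94.
- At 67% retention even a total stop gives 0.929/0.813 = 1.14.
- In (b), a total stop gives 0.95 at 51% and 1.04 at 67%.

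For comparison, in a clinic already at equilibrium a total stop gives (1 - R)/h, or 0.73-0.82, over a year. It is the unfinished ramp-up that hides the stop.

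**Wider assumptions.** Start-up was varied over 4-9 months, retention over 51-67%, and exit times over exponential and Weibull forms.

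| Scenario | (a) | (b) |
|---|---|---|
| Constant starts, no COVID effect | 1.42-2.06 | 1.18-1.41 |
| Starts still rising, no COVID effect | 2.52-4.39 | 1.61-2.12 |
| Constant, then cut by 90% | 0.97-1.44 | 0.96-1.15 |

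**Rejection rates.** A clinic-level simulation used Protocol Table 2 clinic sizes, one late site and two-sided 0.05. Starts were set at 1-2 per week or calibrated to the 0-34 patients per intervention clinic reported for July 2019 in Modification #8. The SD of clinic change was assumed to be 0.05-0.10 days per patient per year. With no COVID effect, all rejections were toward a larger later effect:

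| Test | (a) | (b) | (a), if 2 nurse care managers (NCMs) leave at month 30 and all their excess days end |
|---|---|---|---|
| Change-score t | 69-100% | 35-100% | 17-71% |
| Within-HCS paired t | 56-100% | 28-100% | 9-46% |
| SAP 5.7.1 interaction layout | 13-83% | 1-29% | 1-42% |

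With starts cut by 90%, rejection toward a smaller effect was at most about 5% in every variant, and at most 1% in (a).

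**The case against.** **The size of false rejection is not established.** A reader might infer that the test will reject whenever the intervention works. The documents do not support that, because Modification #23 names no test. The only effect-modification layout available, the interaction test in SAP 5.7.1, can fall below 5% in window (b). This objection stands.

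**Year 2 versus year 3 is not the whole contrast.** That label is exact only for window (a) at five HCSs. Window (b) reduces the drift but does not remove it; the late HCS has more of it.

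**A force acts the other way in (a).** Two NCMs left after the first 6 months, so growth into year 3 is not assured. This stands, but it is a second non-COVID cause and does not restore attribution.

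**Not every result is uninterpretable.** A reader might infer that a significant result in either direction is empty. A decrease in (b), which precedes the NCM departures, would run against the ramp-up bias and would be informative.

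**Absolute sizes should not be quoted.** At 1.5 starts per week and 51% retention the model gives 55.6 rising to 85.1 patient-years. It also gives about 50 patients per clinic at month 16, against the reported 0-34. Only the ratios, which are free of the start rate, should be used.

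**The stakes are limited.** The objective itself is worded in terms of calendar time; COVID enters through the introduction to the objectives and the rationale. It is secondary, depends on a 2-year effect and leaves the main analyses unchanged. Protocol 11.5 promises cautious interpretation of secondary outcomes. All true, but caution does not correct a mislabelled contrast, and requiring a 2-year effect does not remove the drift.

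**Conclusion.** The concern holds in a limited form. The contrast is confounded with time since randomization and, under ramp-up alone, is biased toward a larger effect after 3/1/2020. At the five on-time HCSs the ratio is 1.53-1.68 in (a) and 1.22-1.28 in (b) with no COVID effect. A near-total stop in new starts can appear as no change or even an increase.

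An increase or a null in either window, or a decrease in (a), cannot be attributed to COVID. A decrease in (b) is the one result that runs against the bias.

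The direction rests on the protocol's own statement about slow recruitment and on the outcome definition. The sizes rest on the assumed start profile, exit distribution and retention range. The false-rejection rate stays open, at about 1% to 100%, until a model is specified.

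**What to change.** 1. In Modification #23, describe both contrasts as the change in intervention effect before versus after 3/1/2020; for window (a), say that this is year 2 versus year 3 at five HCSs. Drop the COVID attribution.
2. Add a sensitivity analysis of the quarterly within-HCS difference (PROUD minus UPC) in treatment days, with a term for time since randomization and a test of departure after 3/1/2020. State the model, scale and significance level.
3. Report new treatment starts by quarter and arm alongside treatment days. Constant starts would give a ratio of 1.0 and a 90% cut 0.1, although a rising trend in starts would still need a term.

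The cost is wording and programming; SAP Appendix A already determines covered days for each patient. The added analysis will have low precision with 12 clinics and will depend on the assumed trend shape. The quality-improvement meetings approved on 7/31/2019 (SAP 1.2.2) may also put a break inside the pre-period. It should be presented as exploratory and not as the sole replacement for the planned contrast.

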1.0 LIST OF ABBREVIATIONS

AUD	Alcohol Use Disorders
BMC	Boston Medical Center
BUP	Buprenorphine
CCC	Clinical Coordinating Center
C-IRB	Central Institutional Review Board
CMS	The Centers for Medicare and Medicaid Services
CTN	Clinical Trials Network
CTP	Community Treatment Program
DHHS	Department of Health and Human Services
DM	Data Monitoring
DSC	Data and Statistics Center
DSM-5	Diagnostic and Statistical Manual – 5 th Edition
DSMB	Data and Safety Monitoring Board*
DUA	Data Use Agreement
EDC	Electronic Data Capture
HER	Electronic Health Record
FDA	Food and Drug Administration
FQHC	Federally Qualified Health Centers
FWA	Federal Wide Assurance
GAD	Generalized Anxiety Disorder
GCP	Good Clinical Practice
HCPCS	Healthcare Common Procedure Coding System Codes
HCSRN	Health Care Systems Research Network
HIPAA	Health Insurance Portability and Accountability Act
HSN	Health Systems Node
ICD	International Classification of Disease
ICH	International Conference of Harmonization
IDU	Injection Drug Use or Injection Drug User
IRB	Institutional Review Board
KPCO	Kaiser Permanente Colorado
KPNW	Kaiser Permanente Northwest
KPWA	Kaiser Permanente Washington

KPWHRI	Kaiser Permanente Washington Health Research Institute
LI	Lead Investigator
LN	Lead Node
LNT	Lead Node Team
MA Model	Massachusetts Model
MF	Montefiore
NCM	Clinic-based Nurse Care Manager
NDCs	National Drug Codes
NESARC	National Epidemiologic Survey on Alcohol and Related Conditions
NIDA	National Institute on Drug Abuse
NSDUH	National Survey on Drug Use and Health
NTX	Naltrexone
OBAT	Office Based Addiction Treatment
OBOT	Office Based OUD Treatment
OCD	Obsessive Compulsive Disorder
OTP	Outpatient Treatment Program
OUD	Opioid Use Disorder
PDV	Protocol Deviation
PC	Primary Care
PI	Principal Investigator
PN	Patient Navigation or Patient Navigator
PRISM	Practical, Robust Implementation and Sustainability Model
PT	Participant
PTSD	Post-traumatic Stress Disorder
QA	Quality Assurance
RA	Research Assistant
RE-AIM	Reach, Effectiveness, Adoption, Implementation Fidelity, Maintenance
RRTC	Regional Research and Training Center
SAP	Statistical Analysis Plan
SOP	Standard Operating Procedure
TA	Technical Assistance
UPC	Usual Primary Care (Control Condition)
VDW	Virtual Data Warehouse

-
- * Please note: NIDA CTN's DSMB acts as a scientific review board for all CTN studies, as well as a data monitoring board doing interim reviews of data for low risk studies. Therefore, even though this is a minimal risk study, it has been reviewed by NIDA CTN's DSMB.
-

2.0 STUDY SYNOPSIS

2.1 Study Objectives

Evidence-based treatment for opioid use disorders (OUDs) includes medications, and two medications for OUDs—buprenorphine and naltrexone—can be prescribed in primary care (PC). However, despite the current opioid epidemic and expert recommendations that OUDs should be treated in PC, most PC clinics do not offer treatment for OUDs. This reflects a lack of consensus among health system leaders and clinicians that OUDs should be treated in PC. The overall objective of the PRimary care Opioid Use Disorders (PROUD) trial is to provide information to guide health system leaders in the decision of whether or not to treat OUDs in PC, by evaluating the benefits of implementing a program that integrates high quality OUD treatment into the normal flow of PC.

Specifically, the **primary objective** of the PROUD trial is to evaluate whether implementation of the Massachusetts (MA) Model¹ of collaborative care for management of OUDs in PC (the “PROUD intervention”) increases OUD treatment with buprenorphine or injectable naltrexone, documented in the electronic health records (EHRs) of PC patients, over a 2 year follow-up, as compared to usual PC (UPC).

Our **primary hypothesis** is that there will be a significant increase in the number of patient-days of medication treatment for OUDs documented in the EHR of PC patients in the 2 years after clinics are randomized to the PROUD intervention compared to PC clinics randomized to Usual Primary Care (UPC). This implementation objective reflects whether the PROUD intervention increases initiation of and/or retention in OUD treatment, documented in EHRs within medical settings.

The **main secondary objective** is to test our hypothesis that PC patients with OUDs in the 3 years prior to randomization who receive care in PROUD intervention clinics, compared to those who receive care in UPC clinics, will have fewer days of acute care utilization (including urgent care, emergency department [ED] and hospital care) in the 2 years after randomization. This “effectiveness” objective assesses whether implementation of the MA Model improves patient outcomes.

Other Secondary Objectives include: (1) to conduct observational analyses comparing outcomes of the PROUD intervention clinics to 10 other PC clinics with promising models of OUD care (from the same health systems and 2 other health systems from PROUD Phase 1); (2) to evaluate differences in the impact of the PROUD intervention across sex and race/ethnicity; (3) to test whether the PROUD intervention improves secondary implementation, patient, and process outcomes; and (4) to identify barriers and facilitators to implementation of the MA Model.

2.2 Study Design

The PROUD trial is a hybrid type III pragmatic, cluster-randomized, quality improvement trial. Hybrid type III trials are mixed effectiveness and implementation trials, with greater emphasis on implementation.² The trial will be conducted in 6 health systems across the United States. Randomization is stratified by health system. Each health system has recruited 2 PC clinics (or a cluster of smaller clinics) willing to implement collaborative care for patients with OUDs using a model developed at the Boston Medical Center (BMC) in Massachusetts and spread across federally qualified health clinics in that state (the “MA Model” hereafter). One of the two recruited PC clinics in each health system will be randomized to implement the MA Model, while the other will continue with UPC.

All outcomes will be evaluated using secondary data from electronic health records (EHRs) and/or health insurance claims during the 2 years after randomization.

2.3 Sample and Sample Size

The sample for the trial consists of patients who have visited the selected 12 PC clinics in the 6 participating health systems. Health systems were selected for the PROUD trial based on 1) leadership support for participating in the trial, 2) elements of clinic eligibility such as adequate size and having at least 3 PC providers willing to prescribe buprenorphine in each of the PC clinics, and 3) a demonstrated ability to obtain the secondary data necessary for the PROUD trial measures—specifically days of OUD treatment with buprenorphine and naltrexone and days of acute care utilization. Smaller clinics were eligible if a group of clinics near each other included adequate numbers of patients (target ~10,000 unique patients with visits in a year) and were willing to participate as a single clinic for purposes of this trial, i.e., if selected to implement the MA Model, a nurse care manager (NCM) would be shared.

PC patients 16-90 years old with at least 1 visit to the participating clinics from 3 years before to 2 years after randomization (the 5-year study period) will be included in the trial. The total sample of PC patients in the trial is anticipated to be over 170,000 patients across the 12 clinics, since over 14,000 patients were seen, on average, in each clinic in 2016. The implementation objective is addressed in the full study sample, while the secondary objective is evaluated in the subsample of patients who have EHR documentation of an OUD during the 3 years prior to randomization.

2.4 The PROUD Intervention and Duration

Intervention: Implementation of the MA Model of Collaborative Care for OUDs. The PROUD trial provides financial support to cover the NCM salary and technical assistance (TA) for the duration of the study, but the health system—not investigators—implement the MA Model program as part of quality improvement, and the health system and its clinicians provide all clinical care. One PC clinic or cluster of smaller clinics is randomized to the PROUD intervention in each health system (“*PROUD intervention clinics*” hereafter), and implements the MA Model after randomization. Specifically, the PROUD intervention includes 3 strategies used to implement the Model in Massachusetts.

- (1) Clinic leadership receives funding for at least 1.0 full time equivalent NCM for 2 years after randomization and technical support for recruiting and hiring the NCM. Once hired for the study, the NCM will receive TA from experts in Massachusetts supported by PROUD, but NCMs will be employed and supervised by the health system.
- (2) Experts at BMC who originally developed and disseminated the MA Model will: provide intervention clinics with a MA Model Manual; train PROUD NCMs at BMC for 2 days; and provide the ongoing TA for 2 years after randomization.
- (3) Three PC providers in the PROUD intervention clinic obtain DEA waivers to prescribe buprenorphine for OUDs (if not already waived) and work closely with the NCM to offer high quality PC care for OUD (e.g., medication treatment with buprenorphine or naltrexone with close follow-up to maximize retention in treatment).

Comparison: Usual Primary Care (UPC). Clinics randomized to UPC do not receive any resources or support from the study but are free to improve OUD care in any way they choose. UPC is the appropriate comparison to evaluate the impact of implementation of the MA Model on access to and quality of OUD care because most PC clinics do not currently offer treatment for OUDs, but that could change over the course of the trial. We will qualitatively evaluate OUD treatment at baseline via templated interviews with Site PIs and project managers, and monitor any changes in OUD treatment services over time, in UPC clinics.

